8.1.3 Severity of Adverse Event

A summary of TEAEs by severity will be presented in a table. The severity that will be presented represents the most extreme severity captured on the CRF page. The possible severities are "Mild", "Moderate", and "Severe".

In the TEAE severity table, if a subject reported multiple occurrences of the same TEAE, only the most severe will be presented. Percentages will be calculated out of the number of subjects in the safety population.

The TEAE data will be categorized and presented by SOC, PT, and severity in a manner similar to that described in Section 8.1.1.

Additionally, the related TEAE data will be categorized and presented by SOC, PT, and severity. If a subject reported multiple occurrences of the same related TEAE, only the most severe will be presented. Percentages will be calculated out of the number of subjects in the safety population.

Treatment-emergent SAEs by severity will also be presented in a table.

8.1.4 Adverse Events Leading to Treatment Discontinuation

A summary of the TEAEs with an action taken with study treatment of "Drug Withdrawn" will be presented in a manner similar to that described in Section 8.1.1.

Any TEAEs leading to treatment discontinuation will be presented in a listing for all subjects.

8.1.5 Death

All subjects who have an AE with an outcome of "Death Related to Adverse Event" will be presented in a listing.

8.2 Clinical Laboratory Evaluations

Summary tables will be presented for clinical laboratory test results (hematology, blood chemistry, and urinalysis) at collection visits for subjects in the safety population. Samples for clinical laboratory tests will be collected at Screening, Days 7 to 10, every 14 days up to EoT if clinically indicated, at EoT, at the 6-Week FU if clinically indicated, and at unscheduled visits if clinically indicated. If indicated, these may be done more frequently as follow-up to a laboratory abnormality.

All relevant clinical laboratory tests in chemistry, hematology, and urinalysis will be classified as Low, Normal, and High according to the normal ranges. This categorical data will be summarized in shift tables comparing the extreme results at each visit with those at the baseline visit. Extreme post-baseline results will also be summarized as described in Section 8.2.2. When there are multiple values within a visit for a particular laboratory variable, the worst value will be taken (worst being the smallest value for criteria below a certain threshold or the largest value for criteria above a certain threshold). If a subject has a value below the threshold and above the threshold, the value furthest from the threshold will be chosen.

In data listings, laboratory values will be compared to normal ranges; out-of-range and clinically significant laboratory values will be identified.

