13.2 Exclusion Criteria

A subject will be excluded from participation in the study if he or she meets any of the following exclusion criteria:

- 1. Subject has a fungal disease with central nervous system involvement.
- 2. Subject has a fungal disease of the bone and/or joint that is expected to require >90 days of study drug treatment.
- 3. Subject has an inappropriately controlled fungal infection source (e.g. persistent catheters, devices, identified abscess) that is likely the source of the fungal infection.
- 4. Subject is hemodynamically unstable and/or requiring vasopressor medication for blood pressure support.
- 5. Subject has abnormal liver test parameters: AST or ALT >10 x ULN and/or total bilirubin >5 x ULN.

Note: Subjects with unconjugated hyperbilirubinemia with diagnosis of Gilbert's disease are not excluded.

- 6. Subject has an Apache score >16.
- 7. Subject has serum creatinine >3 times from Baseline (Screening/Treatment Day 1) value.

- 8. Subject has a prolonged QTcF interval (Fridericia's correction: $QTc = QT/(RR)^{0.33}$) >480 ms on the baseline ECG or other abnormalities deemed clinically significant by the investigator that would put the subject at unacceptable risk for participation in the study.
- 9. Subject requires treatment with the prohibited medications listed in Section 23.1 (Appendix A), during the following timeframes:
 - a. Select strong time-dependent CYP3A4/5 inhibitors and CYP3A4/5 inducers during the 14 days prior to enrollment and during study treatment
 - b. Select strong and moderate reversible CYP3A4/5 inhibitors during the 48 hours prior to enrollment and during study treatment
 - c. Select P-gp substrates during the 48 hours prior to enrollment and during study treatment
- 10. Subject is pregnant or lactating.
- 11. Subject has any other condition or laboratory abnormality that, in the judgment of the investigator, would put the subject at unacceptable risk for participation in the study or may interfere with the assessments included in the study.
- 12. Subject has a known hypersensitivity to SCY-078 or any of the components of the formulation.
- 13. Subject has participated in any other investigational study within at least 30 days (or 5.5 halflives of the investigational product) before signing the ICF.
- 14. Subject has received prior treatment with the study drug in a previous trial.

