18.3 Events of Clinical Interest

The following are considered events of clinical interest (ECIs), and must be reported by the site when it becomes aware of the ECI:

- QTc >500 ms or a >60-ms change from Baseline, confirmed by repeat testing
- ALT or AST >8 x ULN, if new compared to Baseline, confirmed by repeat testing
- ALT or AST >5 x ULN for more than 2 weeks and if new compared to Baseline, confirmed by repeat testing
- ALT or AST >3 x ULN and either total bilirubin >2 x ULN or INR >1.5 and if new compared to Baseline, confirmed by repeat testing
- ALT or AST >3 x ULN, confirmed by repeat testing, with the appearance of fatigue, nausea, vomiting, right upper quadrant pain or tenderness, fever, rash, and/or eosinophilia (>5%)]

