8.4 Physical Examination

A general physical examination will be conducted at Screening, EoT, and at the 6-Week FU visits. The physical examination will include an abbreviated assessment of general appearance, skin, eyes, heart, chest, and abdomen.

All abbreviated physical examinations will be classified as Normal, and Abnormal. Any abnormalities noted during the physical examination will be presented in a listing for all subjects.

8.5 12-lead Electrocardiogram

Summary tables will be presented for QTcF for subjects in the safety population. Observed results at the scheduled visits and changes from baseline to post-baseline visits will be presented. All ECG data by subject will be presented in a listing.

9. Interim Analysis and Supplemental Analysis

No interim analysis is planned for this study.

10. Tables, Listings, and Figures

A list of tables, listings, and figures will be maintained outside of this document and may be amended as needed.

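### Liver tests that worsen from an already raised baseline get no categorical summary in the SAP, although the protocol admits ALT/AST up to 10 x ULN and bilirubin up to 5 x ULN

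*SAP*

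**What the plan says.** Protocol 13.2 excludes on liver tests only above a high limit: "Subject has abnormal liver test parameters: AST or ALT >10 x ULN and/or total bilirubin >5 x ULN".

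Protocol 18.3 lists four hepatic events of clinical interest (ECIs), numbered here for reference:

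- Rule 1: "ALT or AST >8 x ULN, if new compared to Baseline, confirmed by repeat testing".
- Rule 2: "ALT or AST >5 x ULN for more than 2 weeks and if new compared to Baseline, confirmed by repeat testing".
- Rule 3: ALT or AST above 3 x ULN with either total bilirubin above 2 x ULN or "INR >1.5 and if new compared to Baseline, confirmed by repeat testing".
- Rule 4: "ALT or AST >3 x ULN, confirmed by repeat testing, with the appearance of fatigue, nausea, vomiting, right upper quadrant pain or tenderness", or with fever, rash or eosinophilia. It carries no newness condition.

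Neither document defines what makes a finding new.

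SAP 8.2 sets the categorical laboratory analysis: "All relevant clinical laboratory tests in chemistry, hematology, and urinalysis will be classified as Low, Normal, and High according to the normal ranges". Shift tables compare the extreme result at each visit with baseline. The SAP adds: "Extreme post-baseline results will also be summarized as described in" Section 8.2.2. The only subsection of 8.2 is 8.2.1, on pregnancy. The next heading is 8.3, and the contents list agrees.

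The SAP text does not mention ECIs. For the ECG, SAP 8.5 says: "Summary tables will be presented for QTcF for subjects in the safety population". It gives values and changes, but no counts against the QTc limits in Protocol 18.3 (above 500 ms, or a change above 60 ms).

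**The concern.** The entry limits lie above the ECI thresholds: 10 against 3, 5 and 8 x ULN for ALT/AST, and 5 against 2 x ULN for bilirubin. An eligible subject can therefore meet rule 1 or rule 3, and exceed the level in rule 2, before the first dose. For that subject the shift table has no higher class to move into, and the same ECI rule may be read as not new. The one summary meant for extreme values has no specification.

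Safety and tolerability is a secondary objective and the only basis that Protocol 20.1 states for 30 subjects. Dosing may last up to 90 days, while the multiple-dose Phase 1 experience cited in Protocol 9.1 covers 28 days. A reader of the report will want to know how many subjects' liver tests worsened, and from what level. No planned categorical table answers that.

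**Working it through.** The documents give no figure to reproduce on this point. The check applies the rules as written to illustrative pairs of values.

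**Inputs.** Entry limits from Protocol 13.2, rules 1 to 3 from Protocol 18.3, and shift classes from SAP 8.2. ALT and bilirubin are in multiples of ULN; above 1 is High.

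**Assumptions.** A finding is new if the rule was not already met at baseline. For rule 2 the two-week duration is taken as met, so a baseline above 5 x ULN counts as already meeting it. For rule 3 only the bilirubin arm is tested. Change = maximum minus baseline; ratio = maximum / baseline.

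| Baseline ALT, bilirubin | Maximum ALT, bilirubin | Rules 1–3 newly met | ALT shift | Change ALT, bilirubin | Ratio ALT, bilirubin |
|---|---|---|---|---|---|
| 9, 1 | 20, 1 | none | High to High | +11, 0 | 2.2, 1.0 |
| 10, 5 | 30, 10 | none | High to High | +20, +5 | 3.0, 2.0 |
| 6, 3 | 7.9, 6 | none | High to High | +1.9, +3 | 1.3, 2.0 |
| 4, 1 | 9, 1 | 1 and 2 | High to High | +5, 0 | 2.25, 1.0 |
| 6, 1 | 9, 1 | 1 | High to High | +3, 0 | 1.5, 1.0 |
| 10, 1 | 30, 3 | 3 | High to High | +20, +2 | 3.0, 3.0 |

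**Shift table.** All six subjects are eligible, and all six show no ALT shift. This does not depend on how newness is read.

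**ECI rules.** In the first three rows none of rules 1 to 3 fires. In the last three a rule fires, because the subject crosses one not met at entry. In all six rows ALT ends above 3 x ULN, so rule 4 would fire if the value were confirmed and a listed symptom or eosinophilia appeared.

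**Sensitivity to the reading of newness.** Suppose instead that any value above the subject's own baseline counts as new. Row 1 then meets rule 1 (20 > 8), row 2 meets rules 1 and 3, and row 3 meets rule 3 (7.9 > 3 and 6 > 2). If the two weeks in rule 2 are counted only from first dose, rule 2 could also fire in all three. The first three rows thus go from none captured to all captured on the definition alone.

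**Effect of graded bands.** Use the protocol's own cut-points: 3, 5, 8 and 10 x ULN for ALT/AST, and 2 and 5 x ULN for bilirubin.

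- Row 1: ALT moves from >8–10 to >10.
- Row 2: ALT moves the same way, and bilirubin moves from >2–5 to >5.
- Row 3: ALT stays in >5–8, but bilirubin moves from >2–5 to >5, and the ALT ratio of 1.3 shows the rest.

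**Size.** One subject in 30 is 1/30 = 3.3%. The number entering above a threshold is not in the documents. An assumed 0 to 5 of 30 gives 0% to 16.7%.

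**The case against.** A reader might infer that liver worsening in these subjects goes unrecorded. The documents do not support that:

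- Protocol 20.8.2 requires laboratory values and their changes from baseline to be summarised, and all safety variables to be listed. SAP Section 3 requires values and changes at each time point, with minimum and maximum among the statistics. In a sample of 30, a rise of 20 x ULN would probably be the maximum in its table.
- SAP 8.2 takes the worst value within a visit and flags out-of-range and clinically significant results in the listings.
- Protocol 18.1 makes a clinically significant laboratory abnormality an adverse event, and SAP 8.1 counts worsening of a pre-existing event as treatment-emergent.
- Rule 4 has no newness condition. Its triggers include nausea and vomiting, which Protocol 9.1 lists among the drug's most frequent events.
- A subject with raised baseline values can still newly meet a rule not met at entry.

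It can also be said that 18.3 is a site-reporting trigger that neither document promises to tabulate. The list of tables is kept outside the SAP and may contain more than the SAP shows. The QTc limits carry no newness condition, so leaving out those counts is missing detail.

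All of this stands, and it limits the point. It does not remove it. Statistics by visit show the size of the largest change, but not how many subjects crossed a level or from what baseline. Under Protocol 16.13, laboratory tests between Days 7 to 10 and end of treatment are done only if clinically indicated, so the by-visit summaries may be sparse. The adverse-event route rests on investigator judgement in an open-label trial, and rule 4 does not cover worsening without symptoms or eosinophilia.

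**Conclusion.** The point holds as a gap in summarisation. For any eligible subject whose ALT, AST or bilirubin is already above normal, the SAP's categorical table must show High to High however far the value rises, and the extreme-value summary cannot be programmed because its section is missing. Rules 1 to 3 may also stay silent for a subject who already meets the same rule at entry. That part depends on the undefined newness condition and is not certain.

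It would be wrong to conclude that such subjects show nothing, or that rule 4 is the only rule left to them. The worsening is recorded; what is missing is a count by baseline level. The effect is 3.3 percentage points per subject, for an unknown number of subjects. No efficacy result is affected. This is an inexpensive improvement to the safety analysis, and worth making because safety is the stated reason for the sample size.

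**What to change.** In SAP 8.2, replace the reference to Section 8.2.2 with a specified table:

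1. Maximum post-baseline ALT, AST and total bilirubin in bands of ULN at the protocol's own cut-points (3, 5, 8 and 10; bilirubin 2 and 5), crossed with the same bands at baseline.
2. Maximum ratio to baseline for each test, summarised and listed.
3. Counts of subjects meeting each threshold in Protocol 18.3, hepatic and QTc, showing separately those who already met it at baseline.

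In the protocol, define when a finding is new relative to baseline, and have the sponsor reconcile the entry limits in 13.2 with the rules in 18.3. No clinical threshold is proposed here. If sites can no longer apply a revised reporting definition, state one in the SAP for the counts. SAP Section 1 allows an amendment before database lock.

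The cost is one or two extra safety tables, almost entirely from data already collected. The INR arm of rule 3 is the exception to check: the laboratory list in Protocol 16.13 shows prothrombin time but not INR, so that arm can be counted only where INR is recorded. Depending on the definition chosen, there may also be a few more ECI reports from subjects with abnormal baseline tests.

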20.8.2 Safety Analyses

All safety analyses will be conducted using the safety population; all safety variables will be listed.

The incidence and severity of treatment-emergent AEs and SAEs and their relationship to treatment will be summarized. AEs will be coded using the Medical Dictionary for Regulatory Activities (MedDRA) Version 19.1 or higher and presented by system organ class and preferred term.

Early discontinuation of study drug treatment will be presented and will include the reasons for and timing of such discontinuations.

Prior and concomitant medications will be summarized; medications will be classified based on the World Health Organization's Drug Dictionary terminology.

Abnormal physical examinations will be listed. Laboratory evaluations will be summarized as observed values and changes from Baseline; shifts with respect to the laboratory reference range will be summarized.

Vital signs and ECG evaluations will be summarized as observed values and changes from Baseline.

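### SAP 8.2 keeps one laboratory value when a subject has both a low and a high result, on an unstated distance scale, so one of two abnormalities drops out of the shift tables

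*SAP*

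**What the plan says.** SAP section 8.2 classifies hematology, chemistry and urinalysis results as Low, Normal or High and states: "This categorical data will be summarized in shift tables comparing the extreme results at each visit with those at the baseline visit". It then deals with repeated measurements: "When there are multiple values within a visit for a particular laboratory variable, the worst value will be taken". Worst is defined by direction: "worst being the smallest value for criteria below a certain threshold or the largest value for criteria above a certain threshold". The next sentence covers a subject with results in both directions: "If a subject has a value below the threshold and above the threshold, the value furthest from the threshold will be chosen".

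The section also plans a second output. "Extreme post-baseline results will also be summarized as described in" points to Section 8.2.2, but the SAP goes from 8.2.1 (Pregnancy) to 8.3 (Vital Signs), and its table of contents likewise shows only 8.2.1 under 8.2.

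On listings, SAP 8.2 says that "out-of-range and clinically significant laboratory values will be identified". Protocol section 20.8.2 says that "all safety variables will be listed" and that "shifts with respect to the laboratory reference range will be summarized"; it contains no rule reducing two directions to one.

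**The concern.** A low and a high result of the same variable are two different safety findings. The SAP's own definition of worst recognises this, because it gives one worst value per direction. The following sentence then collapses the two into one.

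The way it does so is not reproducible. The SAP does not say whether distance is a difference in the reported units, a percentage of the limit, a ratio or log distance, or something else. It also writes of one threshold, although Low and High are defined by two limits. Two programmers could follow the text and put the same subject in opposite columns of the shift table.

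Safety is a secondary objective, and protocol section 20.1 justifies the 30 subjects only by the assessment of safety and tolerability. In a table of that size, one subject is 1/30 = 3.3%. SAP section 7.3.1 plans a subgroup with a neutrophil count below 500, so very low counts are expected in this population.

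**Working it through.** The plan states no figure on this point, so there is nothing to reproduce. The check is how the rule behaves under different distance scales.

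**Inputs.** The rule comes from SAP 8.2. The documents give no normal ranges; those below, and the example values, are assumptions for illustration. Each value's distance is taken from its own limit: low value x from LLN, high value y from ULN.

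**Distances.**
- Plain difference: LLN − x against y − ULN.
- Percentage of limit (as a fraction): (LLN − x)/LLN against (y − ULN)/ULN.
- Log: ln(LLN/x) against ln(y/ULN).

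**Algebra for the plain difference.** A non-negative analyte has x ≥ 0, so the low-side distance is at most LLN. The high-side distance has no cap. If y − ULN > LLN, that is y > ULN + LLN, the high value wins against every possible low value, including zero.

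Under the assumed ranges that point is:
- neutrophils: 7.5 + 1.8 = 9.3 (1.24 × ULN)
- WBC: 11 + 4 = 15 (1.36 × ULN)
- platelets: 400 + 150 = 550 (1.38 × ULN)
- glucose: 100 + 70 = 170 (1.70 × ULN)
- potassium: 5.0 + 3.5 = 8.5 (1.70 × ULN)
- sodium: 145 + 135 = 280 (1.93 × ULN)

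It is a modest elevation for the cell counts and an extreme one for the electrolytes. The disadvantage to low values is therefore a matter of cell counts, and not a general property of the rule.

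**Six illustrative pairs** (low distance v high distance, then the value kept):

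| Analyte (assumed range) | Low, high | Plain difference | Fraction of limit | Log |
|---|---|---|---|---|
| Glucose (70–100 mg/dL) | 35, 180 | 35 v 80, High | 0.50 v 0.80, High | 0.69 v 0.59, Low |
| Neutrophils (1.8–7.5 ×10^9/L) | 0.4, 12 | 1.4 v 4.5, High | 0.78 v 0.60, Low | 1.50 v 0.47, Low |
| Platelets (150–400 ×10^9/L) | 20, 550 | 130 v 150, High | 0.87 v 0.38, Low | 2.01 v 0.32, Low |
| WBC (4–11 ×10^9/L) | 1, 18 | 3 v 7, High | 0.75 v 0.64, Low | 1.39 v 0.49, Low |
| Potassium (3.5–5.0 mmol/L) | 2.4, 5.6 | 1.1 v 0.6, Low | 0.31 v 0.12, Low | 0.38 v 0.11, Low |
| Sodium (135–145 mmol/L) | 118, 149 | 17 v 4, Low | 0.13 v 0.03, Low | 0.13 v 0.03, Low |

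Low result lost: 4 of 6 on the plain difference, 1 of 6 as a fraction of the limit, 0 of 6 on the log scale. High result lost: 2, 5 and 6 of 6. In every cell exactly one abnormality disappears.

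**One subject, three answers.** A glucose of 35 is dropped once the high value exceeds 100 + 35 = 135 (plain difference), 100 × 1.50 = 150 (percentage of limit) or 100 × 70/35 = 200 (log). With a high value of 180 the subject is High on the first two scales and Low on the third.

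**After the change.** If lowest and highest are tabulated separately, all six pairs show both the Low and the High, and no scale is needed.

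**The case against.** Several stronger readings are tempting, and the documents do not support them.

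- *The SAP prescribes distance in reported units.* It does not. Plain subtraction is a natural reading of the sentence, but no scale is named. The supportable defect is the missing scale.
- *The rule systematically hides low values because they are bounded by zero.* That argument needs the plain difference, and even then it is not general: the assumed potassium and sodium pairs keep the Low and lose the High. On the log scale the low side has no bound.
- *The rule applies across up to 90 days of treatment.* The sentence directly follows one about multiple values within a visit, and the shift tables are by visit, so a within-visit rule is the natural reading. The sentence itself refers to a subject and not to a visit, and the extreme post-baseline summary has no rule of its own because Section 8.2.2 is absent. Wider use is therefore possible but not established.
- *A severe low value would go unreported.* The loss is in summary tables only. Listings flag out-of-range and clinically significant values, and the protocol lists all safety variables. Protocol section 18.1 makes any laboratory abnormality the investigator deems clinically significant an adverse event, so it would also enter the adverse event tables if treatment-emergent.

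The case for leaving the rule alone adds that both directions within one visit must be rare. Before follow-up, the only fixed post-baseline laboratory assessments are at Days 7 to 10 and EoT (protocol section 16.13), although repeats after an abnormality are allowed. It also notes that the protocol asks only that shifts be summarized and that the analysis is descriptive. These points limit the importance. They do not answer the core: where both directions occur, a stated rule discards one, by a criterion the SAP does not define.

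**Conclusion.** The point holds as a minor one. The rule removes one of two separate abnormalities from the Low/Normal/High shift tables whenever both occur among the values it is applied to, and the direction removed is left to an unstated scale. On plain differences, low cell counts are at a disadvantage; for other analytes the high value may be lost. The same loss would reach the extreme post-baseline summary if the rule were used there, which the SAP leaves open.

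The size in this trial cannot be calculated: the documents give neither the normal ranges nor how often a subject would have both directions. It is probably uncommon. The 3.3% is what one affected subject would represent among 30, not an estimate of frequency. The worked pairs rest on assumed ranges and values and show direction only. The algebraic bound holds for any non-negative analyte, but only on the plain-difference reading.

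**What to change.** Delete the sentence on values in both directions and replace it with wording such as: *For each laboratory variable with a two-sided normal range, the lowest and the highest value will be summarized separately, per visit and over all post-baseline values, in a low-direction and a high-direction shift table. A subject may appear in both.* This agrees with the direction-specific definition of worst already in SAP 8.2.

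Supply Section 8.2.2 or remove the reference to it. If the sponsor prefers to keep one value, the SAP should state the distance scale, say that each value is measured from its own limit, and say whether the rule applies within a visit or across visits. That makes the table reproducible but still loses one abnormality.

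The cost is a few more tables from the same data: two shift tables instead of one for each two-sided parameter. No new data collection is needed.
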